2.4.3 Exploratory Endpoints

Part A

- Pharmacodynamic assay and/or biomarkers of LAT8881 activity

Part B

- Mechanical QST assessment using Von Frey Aesthesiometer
- Evaluate the effect of intravenous LAT8881, compared with placebo, on VAS radicular pain scores during straight-leg raise nerve stretch
- Bang Binding Index assessment, whereby participant will be asked to record which dosing occasion they believe they got the active IP.
- Pharmacodynamic assay and/or biomarkers of LAT8881 activity.

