2.5 Changes to analyses from protocol

These changes relate to Part B of the study only.

Interim analysis:

The planned interim analysis after at least 10 subjects had completed the study was undertaken after 14 subjects completed the study. The rationale for including 14 subjects within the interim analysis was based on a number of factors, including:

- The observation that 2 of the subjects received less than the full dose (estimated to be 60-65%) due to technical issues with the infusion equipment. Both the sponsor and the PI agreed that it was wise to include at least an additional 2 subjects within the interim analysis
- At the time recruitment approached 12 completed subjects, the recruitment rate was relatively strong, which resulted in 14 subjects completing the study before the interim analysis was initiated.

The planned initial graphical outputs were produced.

No re-estimation of the sample size was undertaken. Based on: (i) the planned graphical outputs, (ii) some additional blinded post-hoc graphical presentations (not discussed in this SAP), (iii) the expectation that 17 subjects were expected to complete the study by 12 May 2023, (iv) dosing an additional 3 subjects to reach the target of 20 could take another 3-6 months, and (v) the inclusion of additional subjects would be unlikely to change any treatment signal in the data to such an extent that continuing recruitment is justified, the recommendation was made to close the study on 12 May 2023, with the last patient last visit then expected on 19 May 2023.

Final analyses:

The data presentation and analysis for the Bang Binding Index assessment has been included in this SAP as it was inadvertently missed in the previous version of the SAP.

After review of the interim analysis outputs where extensive variation in pain scores over time and an unexpected effect of being in the clinic for 24 hours possibly reducing pre-dose pain score on Day 2, particularly for pain at rest, the following decisions were made as to changes to the final analysis outputs.

- Pain at rest:
 - The mean change from baseline from 1 to 2 hours and from 4 to 6 hours are included to provide an easily interpretable summary measure of the pain response profile.
 - The area under the subject profile curve has been removed because it is less meaningful in a clinically useful interpretation of the pain response profile

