 - A scatter plot presenting the paired responses for baseline pain with Placebo on the x-axis, LAT8881 on the y-axis, a diagonal line representing no difference and symbols with different shapes and colours representing each treatment sequence to investigate the possible presence of a Day or treatment carry-over effect.
 - Scatter plot in the same format as for baseline pain, for the mean change from baseline from 1 to 2 hours and for the mean change from baseline from 4 to 6 hours to provide a graphical presentation showing the pattern of any treatment differences in the presence of a possible Day effect.
- Pain on leg raise:
 - All analyses completed for pain at rest will be repeated for pain on leg raise. Given the impact of Day 1 on Day 2 pain at rest scores, pain on leg raise may provide more insight as to the “proof of concept” for LAT8881.

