3. STATISTICAL CONSIDERATIONS

Data analysis will be performed according to [REDACTED] Standard Operating Procedures (SOPs).

The general analytical approach for all endpoints will be descriptive in nature
Unless otherwise stated, the following statistical approaches will be taken:

Continuous variables: Descriptive statistics will include the number of non-missing values, mean, standard deviation (SD), median, minimum, and maximum. The minimum and maximum values will be presented to the same number of decimal places as recorded in the raw data; mean and median will be presented to 1 decimal place more than raw data; and SD will be presented to two more decimal places than the raw data.

Categorical variables: Descriptive statistics will include frequency counts and percentages per category. Percentages will be rounded to one decimal place, with the denominator being the number of subjects in the relevant population with non-missing data.

Imputation: No imputation will be performed for missing data.

Confidence intervals (CIs): If required, CIs will be two sided and will use 95% confidence levels. Any analyses requiring significance testing will use a two-sided test at the 5% significance level.

Unscheduled visits: Unscheduled visits will be excluded from visit-based summary Tables, but will be included in data listings.

Early withdrawal visits Early withdrawal visits will be excluded from visit-based summary tables but will be included in data listings.

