10. Maximum change from baseline will be presented using the same scatter plot format as for baseline scores
11. Mean change from baseline over 1 to 2 hours will be presented using the same scatter plot format as for baseline scores
12. Mean change from baseline over 5 to 6 hours will be presented using the same scatter plot format as for baseline scores

To estimate the difference between LAT8881 and Placebo in the change from baseline "pain now" VAS over all session time points, a generalised linear mixed effects model will be fitted. Fixed-effects will include treatment, session time point and period (i.e. Day) factors; baseline will be included as a covariate. Random effects for participants and participant by period will be included to take into account the repeated measures on each participant and the cross-over nature of the study. The covariance structure for the random effects is assumed to follow a compound symmetry structure. The estimated adjusted (least squares) mean change from baseline for each treatment at each session time, the difference between the treatments, the 95% confidence interval for the difference and the p value for the difference will be presented. A p value of <0.05 will be declared statistically significant. The model assumes no carry-over treatment effect and assumes that any period (i.e Day) effect will affect subjects in both treatment sequences in a similar manner.

The same model will be fitted to the change from baseline "pain on leg raise" VAS scores. As reflected in the scientific literature and regulatory authority guidelines, what constitutes a minimally significant change in baseline pain score can vary from subject-to-subject, whether the pain is acute or chronic, and on the mechanism of the pain. For the purposes of this study, the sponsor considers a 0.9 cm reduction to represent a minimally clinically significant change in pain as reported on the VAS, with the desired target reduction from baseline in the range of 0.9 to 3 cm.

Provocation Assessment with VAS

The pain on leg raise VAS score, change from baseline, percentage change from baseline, maximum change from baseline, mean change from baseline from 1 to 2 hours and mean change from baseline from 4 to 6 hours will be listed for all study participants at each timepoint by treatment sequence as for the "pain now" endpoints. Descriptive summary tables and analyses will be as per the "pain now" endpoints.

Patients general impression of change

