The assessment responses will be listed for all participants by treatment sequence and visit.

The number and percentage of participants in each rating category will be summarised by treatment within period (i.e. Day) and overall.

A graphical presentation will take the form of a heat map with the rating categories for Placebo on the x-axis and the rating categories for LAT8881 on the y-axis. Each cell will contain the percentage of subjects with the corresponding combination of PGIC and will be colour-coded to represent the weight of evidence for the corresponding percentage.

The categories of general impression of change:

- Very much improved
- Much improved
- Slightly improved
- No change
- Slightly worse
- Much worse
- Very much worse

Quantitative Sensory Test (QST) assessment

The Affected and Non-affected dermatome monofilament pain assessment data will be listed for all study participants at each timepoint by treatment sequence.

The number and percentage of participants with pain at each filament will be summarised by type of dermatome and treatment sequence at each timepoint with the number of subjects, mean, standard deviation, median, minimum and maximum by treatment group within treatment period and overall.

Bang Binding Index assessment

The Bang Binding Index assessment identifying which Day the subject believed they were treated with the active treatment will be listed for all study participants.

The number and percentage of participants who correctly identified when they were using active treatment will be presented by treatment sequence and overall.

Sub-group Assessment of Demographic Factors

The contribution of demographic factors (listed in 7.1.1 above) to any differences in efficacy between treatment groups will be investigated.

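### The p<0.05 rule for pain now also covers exploratory leg-raise pain, which was given the same analyses after the interim review, so there are two routes to a significance claim

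*SAP*

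**What the plan says.** **Rank of the endpoints.** Pain now is the only Part B primary endpoint (protocol synopsis; SAP 2.4.1). The effect of LAT8881 "on VAS radicular pain scores during straight-leg raise nerve stretch" is listed under SAP 2.4.3 Exploratory Endpoints, and the protocol synopsis ranks it the same way. PP is the primary population for efficacy (protocol 21.2.2 and 21.5; SAP 4.1.2). Results are also given for the full analysis set (FAS).

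**Change after the interim.** SAP 2.5 introduces its changes to the final outputs with "After review of the interim analysis outputs where extensive variation in pain scores over time" and with a possible effect of the clinic stay on Day 2 pre-dose pain. One change reads "All analyses completed for pain at rest will be repeated for pain on leg raise". The reason given is that Day 1 affected Day 2 rest scores, so that "pain on leg raise may provide more insight as to the" proof of concept for the drug. SAP 15 shows that the planned interim figures included leg-raise group means by time point and coded sequence.

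**Significance rule.** SAP 3 states "Any analyses requiring significance testing will use a two-sided test at the 5% significance level". SAP 11.1.1 describes the model for pain now and adds "A p value of <0.05 will be declared statistically significant". The next paragraph begins "The same model will be fitted to the change from baseline", there for the leg-raise score, and the provocation paragraph says that leg-raise analyses follow those for pain now. Neither section gives a testing order, a multiplicity adjustment or a success criterion.

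**The concern.** An exploratory score now has the same model and the same licence to be called significant as the primary endpoint. The extension was decided after outputs on both scores had been reviewed, and the stated reason links leg raise to proof of concept. If pain now shows nothing and leg raise gives p<0.05, the SAP as worded allows the report to say that a statistically significant effect was found. Nothing in SAP 11.1.1 tells the reader that this result ranks lower. In a proof-of-concept trial, such a sentence could steer later development.

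**Working it through.** The documents give no family-wise error rate, power or sample-size calculation, so there is no derived figure to reproduce. The only stated figure is 5% two-sided per test.

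**Step 1: how many tests does the written model give?** SAP 11.1.1 lists the fixed effects as treatment, session time point, period and baseline. Apart from the random effects, the expected change is

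E(change) = μ + τ·treatment + γ(time) + π·period + β·baseline.

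The LAT8881 minus placebo difference in adjusted means at time t is then τ for every t, because γ(time) cancels. A fit of these fixed effects to invented data for 17 subjects and 12 times confirmed this: the difference was -0.0181 at all 12 times. With a treatment-by-time term added, the same data gave differences from -0.4478 to 0.4729. As written, there is therefore one overall contrast per score, or two in PP.

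**Step 2: chance of at least one false significant result with two tests.** With c = 1.96 and correlation ρ between the two test statistics (an assumption, since the documents give none):

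- either direction: 1 - P(|Z1|<c and |Z2|<c)
- drug-favouring direction: 1 - P(Z1<c and Z2<c), by symmetry

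For ρ = 0 these are 1 - 0.95² = 0.0975 and 1 - 0.975² = 0.0494. The other rows come from the bivariate normal distribution.

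| ρ | Either direction | Drug-favouring |
|---|---|---|
| 0 | 9.75% | 4.94% |
| 0.3 | 9.51% | 4.76% |
| 0.5 | 9.07% | 4.54% |
| 0.7 | 8.35% | 4.17% |
| 0.9 | 7.04% | 3.52% |
| one test only | 5.0% | 2.5% |

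A simulation with 17 paired differences and t tests (40,000 runs per setting, as a stand-in for the mixed model) gave 4.9-5.2% for one overall test and 7.9-9.9% for two.

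**Step 3: if a treatment-by-time term were added.** SAP 11.1.1 asks for adjusted means for each session time, which could lead an analyst to add the term and read a p value at each of the 12 times. In the same simulation, with correlation between times from 0.9 down to 0.3, the chance of at least one p<0.05 was about 14-40% for one score and about 21-64% for both. These figures do not apply to the model as listed.

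**Step 4: what a rule would restore.** One named test gives 5%. A fixed sequence (pain now, then leg raise only if pain now succeeds) gives at most 5%. Two tests at 0.025 each give 1 - 0.975² = 4.94% if independent, and at most 5% at any correlation.

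**The case against.** The case for leaving the text alone is substantial.

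- *The study is exploratory.* Protocol 21.1 specifies no formal hypotheses and already carries the p<0.05 convention. SAP 2.2 reports no formal sample-size calculation, and SAP 3 calls the general approach descriptive. No study-wise alpha exists to be breached. This stands, and it limits the point to interpretation. It does not explain why a descriptive study needs a declaration of significance on two scores.
- *The hierarchy can be worked out.* There is one primary endpoint, one primary population and, as written, one contrast per score. This largely stands, but no sentence confines the declaration to that contrast, and the leg-raise paragraph takes over the whole analysis.
- *The interim was masked and the change is disclosed.* Subject numbers were scrambled and sequences coded A and B, and SAP 2.5 states openly when and why leg raise was extended. The recorded reason is a Day effect on resting pain, not a treatment difference. A reader might infer that leg raise was chosen because it looked favourable; the documents do not show that. Coding hid the direction of the A-B contrast, but its size in 14 of about 17 expected completers could still be seen.

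A reader might also infer a much larger error rate. Three such readings are not supported:

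- Twenty-four per-time tests need an interaction term that SAP 11.1.1 does not list. The per-time treatment differences elsewhere in the plan are graphs or descriptive summaries.
- Counting subgroups as eight independent tests (1 - 0.95^8 = 34%) goes beyond the text, which says only that the contribution of demographic factors "to any differences in efficacy between treatment groups will be investigated". No test is named, and several listed factors overlap, such as age and date of birth.
- FAS adds little as a further chance, because PP is already ranked first.

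**Conclusion.** The point holds at modest size. The significance rule covers two overall tests, one of them on an exploratory score whose analyses were extended after the interim review. The chance of at least one false significant result is about 7-10% instead of 5%, or about 3.5-5% instead of 2.5% in the drug-favouring direction. This assumes no drug effect, the model as listed, PP as the deciding population, and a correlation between the two tests of 0 to 0.9. The rate would be higher only if a treatment-by-time term were fitted and p values read at each time, which the wording leaves open.

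The documents do not show that leg raise has replaced the primary endpoint: SAP 2.4.3 still ranks it as exploratory. Nor can it be checked whether the mixed model itself predates the interim, since the earlier SAP is not available and SAP 2.5 does not list the model as a change. What SAP 2.5 does record as decided after the interim is the extension of the pain-at-rest analyses to leg raise.

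**What to change.** In SAP 11.1.1:

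1. Name the overall LAT8881-placebo contrast for pain now in the PP population as the only result that may be declared statistically significant.
2. State whether a treatment-by-time term is fitted. If it is, define the overall contrast explicitly and treat per-time differences as descriptive.
3. Report leg raise, any per-time differences, FAS and subgroup results as estimates with 95% confidence intervals and nominal p values, labelled exploratory or supportive.

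SAP 2.5 already says that the leg-raise extension followed the interim review, so no new disclosure is needed there. If the sponsor wants to keep a formal claim on leg raise, a fixed sequence after pain now, or 0.025 for each score, would also hold the rate at or below 5%.

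The cost is SAP wording only. No data or analysis is lost. The sponsor gives up a significance claim on leg raise, an endpoint that its own SAP ranks as exploratory.

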12. SAFETY

Analysis Set: Safety Population

The following Safety analyses will be performed if there is enough data to warrant the analysis tables. If there is not enough data, we will write a paragraph describing the safety events.

12.1 Adverse Events (AEs)

AEs will be coded using the current version of the Medical Dictionary for Regulatory Activities (MedDRA, version 24.1) by system organ class (SOC) and preferred term (PT), classified from verbatim terms.

All AEs recorded during the study will be listed, grouped by participant and treatment group.

A Treatment Emergent Adverse Event (TEAE) is defined as any untoward medical occurrence reported or observed after the start of dosing with study drug and prior to the End of Study visit. Conditions present before the first dose of study drug that increase in severity after the first study drug administration will also be considered TEAEs. Where an AE start date is partially or fully missing, and it is unclear as to whether the AE started after treatment administration, it will be assumed to be a TEAE.

AE summaries will be restricted to TEAEs only.

An overview summary table of TEAEs will be provided for:

- Part A by treatment group and overall
- Part B by treatment within sequence, by treatment and overall

Table will include number of participants reporting at least one of the following:

- TEAE
- Grade 3+ TEAE
- Related TEAE
- Serious TEAE
- Serious and related TEAE

Number of participants discontinued from treatment due to a TEAE

Number of participants withdrawn from the study due to a TEAE

Number of deaths

For the TEAE summaries, participants who experience the same TEAE more than once will be counted only once for that event within each category (PT, SOC or overall).

The number and percentage of participants experiencing a TEAE, will be summarised for each SOC and PT by cohort and overall for the following categories of events, by severity:

- All TEAEs
- All TEAEs related to the study drug
- All Grade 3+ TEAEs
- All serious TEAEs
- All serious TEAEs related to the study drug

The number and percentage of participants experiencing a TEAE will be summarised for each SOC and PT by maximum severity and cohort for all TEAEs and all TEAEs related to study medication. If a participant experiences the same AE at more than one severity grade, the most severe rating or the stronger causal relationship to investigational product will be given precedence. Only severities that are populated will be reported.

12.2 Prior and Concomitant Medication

Prior and concomitant medications will be coded using The WHO Drug Dictionary September 2021 release, with Preferred Name (PN) and Anatomical Therapeutic Chemical (ATC) code.

A prior medication will be defined as a medication that was commenced prior to the first study drug administration. A concomitant medication will be defined as a medication taken after first study drug administration. Medications stopped on the same day as first study drug administration will be considered as prior medication only.

Prior and concomitant medication summaries will be presented in separate tabulations. All medications will be listed for each participant, with each medication flagged as to whether they are a prior medication, concomitant medication, or both. For part A, prior medications will be presented overall and concomitant medications will be presented by treatment group and overall. For part B, prior medications will be presented by treatment sequence and overall, and concomitant medications and safety measure summaries will be presented by treatment within each treatment period and overall.

Table summaries will be presented using frequency counts and percentages. For the summaries of prior and concomitant medications, subjects who take the same medication (in terms of the lowest level ATC) more than once will be counted only once for that medication.

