### 9.6.5. Prior and Concomitant Medications

Prior medications are those medications that are initiated and stopped prior to first study drug administration, while concomitant medications are medications taken at least once after first study drug administration. All medications stopping on the same day as first study treatment will be considered as concomitant medications. SARS-CoV-2 vaccination is acceptable, if > 2 week prior to dosing.

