## 18. PROHIBITIONS AND RESTRICTIONS IN THE STUDY

### 18.1. Prohibited medications

Participants must abstain from alcohol for 24 hours prior to each dosing occasion. Illicit drugs are prohibited. Participants should also avoid caffeine for 48 hours and grapefruit juice for 24 hours prior to arrival to study visit.

Use of prescription or over the counter medications and vaccines are prohibited within 14 days of investigational product administration and during the study, with the exception of current medications provided the dose has been stable for at least 14 days, contraceptive medications, paracetamol, oral non-steroidal anti-inflammatory agents and vitamins;

Participants should also not receive any other investigational products during the study.

Participants should also not initiate any new exercise or physical therapy regimens during the study. Exercise and physical therapy regimens that were in place at the Screening visit may be continued in a stable manner during the study.

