 - Events started prior to the Day 1 study drug administration will only be considered as Medical History.
 - If start date is after Day 1 study drug administration, then it will be assigned to the treatment received in Period 1.
 - If start date is after the Day 2 study drug administration, then it will be assigned to the treatment received in Period 2.
- Protocol Deviations:
 - If date is before Day 1 then it will be assigned to Screening
 - If date of deviation is after Day 1 study drug administration, then it will be assigned to the treatment received in Period 1.
 - If start date is after the Day 2 study drug administration, then it will be assigned to the treatment received Period 2.
- Concomitant Medications:

- Based on start and end dates – if subject was on medication within a given period then that medication will be summarised within that period. If subject took medication across both periods then it would be counted in both treatment columns.
- Treatment Exposure will be summarised by sequence and total

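### SAP 12.2 reverses the protocol's rule for medications stopped on the first dosing day, so Day 1 analgesic use can be left out of the concomitant medication tables

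*SAP*

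**What the plan says.** Protocol 9.6.5 has three rules:

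- Prior: "Prior medications are those medications that are initiated and stopped prior to first study drug administration".
- Concomitant: "concomitant medications are medications taken at least once after first study drug administration".
- Same day: "All medications stopping on the same day as first study treatment will be considered as concomitant medications".

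SAP 12.2 also has three:

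- Prior: "A prior medication will be defined as a medication that was commenced prior to the first study drug administration".
- Concomitant: "A concomitant medication will be defined as a medication taken after first study drug administration".
- Same day: "Medications stopped on the same day as first study drug administration will be considered as prior medication only".

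SAP 12.2 puts prior and concomitant medications in separate tables. In Part B the prior table is by treatment sequence and the concomitant table is by treatment within period. Every medication is also listed with a flag for prior, concomitant or both. For Part B, SAP 3.2.6 allocates concomitant medications by start and end dates: "if subject was on medication within a given period then that medication will be summarised within that period".

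Protocol 18.1 exempts several items from its medication ban, among them "paracetamol, oral non-steroidal anti-inflammatory agents and vitamins". SAP 2.5, which lists changes from the protocol, covers the Part B interim analysis and final outputs. It does not mention the medication definitions.

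**The concern.** The two same-day rules are opposites, and the change is not declared. The SAP sentence also does not fit the two definitions before it. A drug first taken after the infusion is concomitant and not prior under those definitions, but becomes prior only if it is stopped that day.

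This matters because the drugs most likely to be taken once and stopped include simple analgesics, which bear directly on a pain score followed for six hours. SAP 2.5 reports that pre-dose pain on Day 2 may have been lower than expected. It attributes this to time spent in the clinic and adds outputs to look for Day and carry-over effects. An analgesic taken later on Day 1 is an alternative explanation that a reader would want to check, the more so because the overnight stay could be waived. The concomitant table by treatment within period is the natural place to look, and the SAP sentence removes single-day Day 1 use from it.

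**Working it through.** There is no planned figure to reproduce. The check applies each document's rules to medications defined by when they start and stop.

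| Case | Protocol 9.6.5 | SAP 12.2, first two definitions | SAP 12.2, same-day sentence | Result |
|---|---|---|---|---|
| 1. Stopped before Day 1 | Prior | Prior | Not engaged | Agree |
| 2a. Commenced earlier, last taken on Day 1 before the infusion | Concomitant by the same-day rule, although the definition of prior also fits | Prior | Prior only | Conflict with the protocol's same-day rule |
| 2b. Commenced earlier, last taken on Day 1 after the infusion | Concomitant | Both | Prior only | Conflict |
| 3. First taken after the Day 1 infusion, stopped that day | Concomitant | Concomitant, not prior | Prior only | Conflict |
| 4. Started after the Day 1 infusion, stopped on Day 2 or later | Concomitant | Concomitant | Not engaged | Agree |
| 5. Single dose after the Part B Day 2 infusion | Concomitant | Concomitant | Not engaged | Agree |

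**Part B.** Cases 3 and 5 are the same behaviour one day apart. Case 3 is left out of the concomitant table and case 5 is counted. The omission therefore falls on Period 1 only.

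**Part A.** SAP 2.1.1 has two groups of four, each with 3 on LAT8881 and 1 on placebo on each dosing day. Day 1 therefore has 2 × 3 = 6 participants on 0.8 mg/kg and 2 × 1 = 2 on placebo. Single-day Day 1 use is lost for both. Medications that continue past Day 1, or are taken on later days, are still counted.

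**Size.** Let u1 and u2 be the amounts of single-day, post-infusion use on Part B Days 1 and 2. The share of that use missing from the table is u1/(u1 + u2). Neither document gives u1 or u2, so the share could lie anywhere from 0 to 1. It equals one half only if use is assumed equal on the two days.

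**Efficacy model.** The mixed model in SAP 11.1.1 has treatment, time point and period as fixed effects, with baseline as covariate. It has no medication term, so its estimate does not depend on this classification.

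**The case against.** The strongest reply is that the SAP does not clearly drop these drugs. SAP 3.2.6 would place a medication taken in Period 1 in the Period 1 column. The same-day sentence can also be read as a tie-break for drugs commenced before dosing, since a drug first taken after the infusion does not meet the SAP's definition of prior. A programmer could count case 3 correctly on either ground. This stands in part: the outcome depends on which sentence is followed. But SAP 3.2.6 only allocates medications to periods and does not expressly override the prior-only class. Even on the tie-break reading, case 2b is still misclassified.

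A reader might also infer more than the documents support:

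- **That the drugs disappear from the record.** They do not. They stay in the listings and would appear in the prior table.
- **That the Part A 0.8 mg/kg column is emptied.** It is only thinned. Ongoing medications and later use remain, and Day 1 placebo recipients lose entries too.
- **That the rule favours one treatment.** Both treatments are given in Period 1, with 10 participants planned per sequence (SAP 2.2). The omission loses information and distorts Period 1 against Period 2, but does not by itself favour LAT8881 or placebo.
- **That about half of single-day use is lost.** That only restates an assumption of equal use on both days.

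Inclusion criterion 14 also asks participants to keep analgesic use stable or decreased from the week before dosing to the week after. This should limit new single doses, but does not rule them out.

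**Conclusion.** The point holds as an undeclared reversal of a protocol definition that also makes the SAP inconsistent with itself. Applied as written, SAP 12.2 leaves out of the concomitant tables any medication stopped on the first dosing day, including one taken after the infusion. The Part B table then under-counts Period 1 relative to Period 2 and is a poor check on whether analgesic use could explain either day's pain scores. In Part A, Day 1 use is under-counted for 0.8 mg/kg and placebo.

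The conclusion assumes that the same-day sentence is programmed literally. If SAP 3.2.6 or the second definition is followed instead, the effect is smaller. The number of medications affected is unknown. The harm is confined to descriptive tables and the judgements drawn from them. The sentence should be corrected, but it does not put the efficacy estimate in doubt.

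**What to change.** Replace the same-day sentence in SAP 12.2 with the Protocol 9.6.5 rule. Class as concomitant any medication taken at or after first dosing and any medication stopping on the day of first dosing. Flag it as both if it was commenced before the first dose. SAP 3.2.6 can then be applied to Part B as it stands.

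The sponsor may prefer to split Day 1 by clock time, so that a drug last taken before the infusion (case 2a) counts as prior. That is defensible, but it is not the protocol's same-day rule. It should be stated as a departure and justified in SAP 2.5.

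The cost is one sentence and one derivation, with no new data. The concomitant tables may become slightly longer.
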